#### **BACKGROUND AND SIGNIFICANCE**

Glaucoma Epidemiology and Glaucoma Disparities. The prevalence of glaucoma in the United States (US) is expected to grow from the current 2.7 million to 4.2 million by 2030. Researchers estimate that 50% of people remain undiagnosed, so 2.1 million US citizens will remain undiagnosed in 2030 with current screening methods. Health care disparities exist with African Americans being three times more likely to have glaucoma, five times more likely to have unilateral blindness from glaucoma, and twice as likely to have bilateral blindness from glaucoma, compared to Caucasians. The National Academy of Science, Engineering & Medicine (NASEM) has recommended a call to action to make eye health a population health imperative. One target is to improve eye care for underserved populations that include African Americans and people with lower socio-economic status. There is a critical need to address disparities in population eye care and to minimize glaucoma-related vision loss.

Programs screening for glaucoma in impoverished communities have identified glaucoma and glaucoma suspect cases at much higher rates than within the general population. In Philadelphia, Pennsylvania, community-based comprehensive eye exams identified incident glaucoma in 17% of those screened and incident glaucoma suspects in 21% of those screened. Similarly, in Birmingham, Alabama, community-based comprehensive eye examinations identified incident glaucoma in 19% of those screened and incident glaucoma suspects in 23% of those screened. This demonstrates the scientific rigor of focusing glaucoma screening on populations at high risk of the disease as a critical first step to changing the prevalence of un-diagnosed glaucoma and subsequent glaucoma-related vision loss.

We hypothesize that implementing a telemedicine platform will decrease the glaucoma screening gap. Telemedicine can take specialty glaucoma services to the locally trusted environment of primary care community clinics. Telemedicine involves the electronic communication of medical information from one site to another for review by physicians specializing in the conditions being assessed. Screening patients does not require an in-person specialist encounter, so evidence-based specialty care becomes accessible in geographically remote areas and does not require patient transportation over long distances. Therefore, telemedicine helps overcome logistical and psychosocial barriers to care. Patients are accustomed to finding transport to their community clinic, and social workers in these clinics can help patients access transportation resources to the clinic. Thus, a telemedicine approach can improve access to glaucoma screening, currently lacking for these communities.

#### **OBJECTIVE**

Our objective is to overcome a key set of critical barriers to glaucoma care by addressing the logistical and psychosocial issues that limit the access of vulnerable populations; by enhancing

and expanding our current partnerships with community clinics: Hope Clinic (Ypsilanti, MI), and a federally qualified health center Hamilton Community Health Network (Flint, MI), to enable local screening for glaucoma and other potentially blinding diseases among vulnerable populations using a telemedicine approach.

#### SPECIFIC AIM/HYPOTHESIS

Aim 1: (Phase 1- HUM 00173023) Use community-engaged research strategies to overcome key logistical and psychosocial barriers to accessing glaucoma care for uninsured and underinsured adults. To engage communities in glaucoma program development, we will create a Community Advisory Board (CAB) to solidify a trusting partnership between the University of Michigan, the Hope Clinic, Hamilton Community Health Network. We will conduct semi-structured interviews with patients and community stakeholders to understand barriers to eye care and inform program development and implementation.

Aim 2: (Phase 2- HUM 00169371) Develop a sustainable telemedicine model for glaucoma screening and care in community clinics. We hypothesize that a validated Veteran's Affairs (VA) telemedicine glaucoma screening program will identify a higher prevalence of glaucoma in primary care community clinics than screening the general population. We will test this hypothesis by implementing: (1) an automated technician-lead glaucoma screening with the VA protocol in the Hope and Hamilton partner community clinics for approximately 5,800 participants over 4 years; (2) remote ophthalmologists' grading of glaucoma screening tests for diagnosis and management; (3) a one-month follow-up visit with the technician to deliver low-cost eyeglasses and to educate and arrange ophthalmology care for participants who screen positive for eye disease; and (4) assess a 24-month change in vision and vision-related quality of life among participants screened during Year 1.

Aim 3: (Phase 2- HUM 00169371) Integrate personalized glaucoma education and counseling during the technician visit and test the behavioral intervention's impact on adherence to follow-up care with an ophthalmologist. We hypothesize that personalized eHealth education and motivational-interviewing-based counseling will improve adherence to glaucoma follow-up care compared to standard education delivered by a trained staff member. We will test our hypothesis in a randomized controlled trial with participants (n=400) from Aim 2 who have glaucoma or suspected glaucoma. We will make iterative refinements to our existing evidence-based, individualized counseling/eHealth glaucoma education program with a focus on adherence to follow-up recommendations based on learning in Aim 1. The primary outcome is the proportion of participants attending the recommended physician appointments within three months. Secondary outcomes include glaucoma knowledge, satisfaction with communication, and confidence in asking the ophthalmologist questions. Program economic efficiency will be assessed.

#### **METHODS**

Aim 1: Use community-engaged research strategies to overcome key logistical and psychosocial barriers to accessing glaucoma care for uninsured and under-insured adults

# and develop and implement a telemedicine-based glaucoma screening program in the community clinics.

In Aim 1, we will use community-engaged research to understand community-specific barriers to glaucoma screening uptake and follow-up glaucoma care. We will use semi-structured interviews with key-stakeholders, including patients and providers, to understand how best to implement glaucoma screening and follow-up care in community clinics that are both located in cities with high rates of poverty. We will obtain informed consent and interview up to 50 people including patients with glaucoma, eye care providers, and community clinic staff.

Semi-structured interviews will explore: (1) community-specific barriers to eye care and follow-up, (2) how a telemedicine glaucoma screening program could be best implemented to meet people's needs, and (3) what educational components would be most salient in motivating people to return for glaucoma follow-up care.

We will form a Community Advisory Board (CAB) comprised of leaders from the Hope and Hamilton clinics, providers from the clinics, patients from the community and university researchers. The board will meet quarterly throughout the grant period to refine, implement, analyze, and discuss how to sustain the interventions. Following written informed consent, CAB members will be asked to take a brief survey at each meeting. A crosslink file containing survey participant names with a study identifier will be kept to correlate member responses over time.

# **Data Analysis**

Qualitative methodology: We will use a semi-structured interview guide to inform the conversation. All interviews will be audio-recorded and transcribed verbatim. Transcripts will be investigated for major themes by two researchers using grounded theory, which uses inductive reasoning to analyze what participants said without coming to the interviews with a preconceived notion as to how the data should be categorized. Key ideas and phrases expressed by the participants will be categorized as codes. A code book is then generated as a team. Five transcripts will be coded, and inter-coder reliability will be calculated using qualitative software. The two coders will then code the transcripts and major themes will be identified. This information will inform program development and implementation.

# Aim 2: Develop a sustainable telemedicine model for glaucoma screening and care in community clinics.

In Aim 2, we will deploy a telemedicine glaucoma screening program in the primary carebased community clinics. We will offer both free glaucoma screening and a free eyeglasses exam.

Telemedicine-based vision and glaucoma screening protocols developed and validated by the US Veterans Affairs (VA) Medical Center will be used. Following the Technology-Based Eye Care Services (TECS) program, an ophthalmic technician is based permanently in a primary care clinic and will operate out of a room containing only essential ophthalmology equipment (i.e., no slit lamp). The technician will test the patient's vision using automated processes (e.g. autorefractor, hand-held tonometer, fundus photographs,

and optical coherence tomography). Data will be transmitted via a secure electronic health record (EHR) to a remote ophthalmologist. The ophthalmologist will review the data, develop an assessment and plan including prescribing eyeglasses and follow up for suspected eye diseases, if identified. We will use the secure image storage and reading platform at the UM Kellogg Eye Center, to transmit imaging data from community clinic sites to the University for images to be assessed.

# **Research Design**

#### **Recruitment:**

Participant selection at Hope & Hamilton clinics

Inclusion criteria:

≥18 years of age

#### Exclusion criteria:

Significant eye pain ( $\geq 8$  out of 10)\*

Sudden decrease in vision (within 1 week)\*

Double vision that doesn't stop when you blink and stops no matter what eye you cover (not blurred, but seeing 2 objects\*

Pregnant women

**Prisoners** 

Cognitive impairment- unable to give an ocular and social history

Moving outside of Michigan or driving distance to the clinic within 6 months

\*if any of these symptoms are present, the patient will be directed to the primary care physician staffing the clinic

We will focus on recruiting people with diabetes and African Americans over the age of 50. We will recruit participants by calling people prior to their scheduled appointments at the primary care and dental care clinics. We will describe the study and let them know they can participate on the day of their scheduled appointment. Additionally, when the ophthalmic technicians' have availability, they will encourage referrals for diabetic patients seen in clinic that day. We will publicize the program in both free clinics using print media to open the program to self-referrals. To make the program more widely known in the community, we will have information about the program on the clinic websites.

Study staff will become registered clinic volunteers. This will allow them access to clinic space and electronic records.

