**Post Program Participant Interview:** We will ask up to 75 participants to participate in a post program interview to identify program components that are helpful/unhelpful and areas for improvement. We will randomly contact English speaking participants within our study database that agreed to be contacted for future studies. The study consent document contains an additional signature section for participants to consent/not consent contact for future research. Selected participants will be contacted by phone, or in-person following their last appointment. Interviewers will follow the survey interview guide. Interviews will be conducted via in-person at the clinics, telephone, or UM Zoom. Participants will receive a \$20.00 Visa Gift Card or check by mail or in-person. Additionally, interviews will be recorded, transcribed, and stored on a secure UM server. Qualitative software such as Dedoose may be utilized. 1/24/2023 English post program interviews have been completed.

**Evaluation of "No-show" Appointments:** We will evaluate our high (approximately 35%) no-show and last-minute cancelations rates at this community clinic study (Hope & Hamilton

Community Clinic). The SIGHT study is open to non- clinic patients, therefore, potential participants may or may not be clinic patients. We will only review data of the SIGHT study "no shows" and will not include the clinics appointment "no shows". When potential participants contact the SIGHT team, the team member reviews the recruitment script that describes the study. Following this discussion and verification of study eligibility, a medical record number (MRN) in MiChart is created for those that do not already have an MRN. The SIGHT study baseline appointment is then made within the MiChart system. This process is completed prior to consent.

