#### **Outcomes**

Primary: The primary outcomes will be the number of participants screened and the prevalence of glaucoma/glaucoma suspect diagnosis and the cost per case of detected disease.

Secondary: 1a) Prevalence of other eye disease: visual impairment (visual acuity in the better seeing eye <20/40) on screening presentation, refractive error, cataract, diabetic retinopathy, and age-related macular degeneration. Prevalence will be determined by dividing the number of cases of disease on initial screening exam by the total number of participants who received screening each year. 1b) Incident disease will be estimated by

assessing the number of new cases of eye disease among the participants screened in the first year who returned for repeat screening in the third year. 2) The mean time since last eye exam: will be reported for the entire cohort of new patients seen for screening. The proportion of patients whose last eye exam was >2 years prior will be calculated for the cohort. 3) Vision related quality of life (NEI VFQ 9) will be assessed for all participants. The associations of vision related quality of life with eye disease diagnosis and demographic variables will be assessed. The 2-year change in vision and vision related quality of life will be measured for all participants screened in the first year of the program and re-screened in Year 3.

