Sample Size: Approximately 5,000 patients access the Hope Clinic per year and 25,000 patients access the Hamilton clinic per year. One technician will be assigned full-time to Hamilton. The other technician will split time between Hope (60%, Tuesday, Wednesday, Thursday) and Hamilton (40%, Monday and Friday) because there is such a higher volume of patients to screen at Hamilton and the Hope Clinic is not open on Mondays or Fridays. The clinic equipment at Hamilton will be set up to be used by both technicians. A typical day for each technician will include 5 screenings and 5 one-month follow-up visits. In the first 2 years (48 weeks each) at each site, all screenings will be of new or 1 year follow up patients. In the 3rd year, 2 will be new and 3 will be one or two-year re-screening visits. At Hope, the technician has capacity for 2448 new screenings and 432 repeat screenings in 4 years. At Hamilton, the technicians have capacity for 4872 new screenings and 1008 rescreenings in 3.5 years. Thus full capacity is 7320 new screenings and 1440 re-screenings. Operating at just 80% capacity enrolls over 5,800 patients for new screenings including over 1100 with 2-year re-screenings to determine impact on longer term visual acuity and visual function.

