#### **Data Analysis**

Primary Outcome Analysis: The primary outcomes will be the number of participants screened, the prevalence of glaucoma/glaucoma suspect diagnosis and the cost per case of detected disease. related macular degeneration) will be summarized similarly. Based on the anticipated sample size (n=5800), the margin of error is at most 1.2 percentage points for the overall prevalence (but could be larger for annual and by-site estimates).

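### Aim 2 states its hypothesis for primary care clinics, but the pooled prevalence is a yield among everyone screened, and its margin covers only the sampling error of that yield

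*Protocol*

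**What the plan says.** Under Specific Aim/Hypothesis, Aim 2 expects that the telemedicine programme "will identify a higher prevalence of glaucoma in primary care community clinics than screening the general population". The Aim 2 Outcomes section lists among the primary outcomes "the prevalence of glaucoma/glaucoma suspect diagnosis and the cost per case of detected disease". The Sample Size paragraph opens with the clinics' own volume: "Approximately 5,000 patients access the Hope Clinic per year and 25,000 patients access the Hamilton clinic per year".

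The Recruitment text under Research Design gives several ways in:
- telephone calls before scheduled primary care and dental appointments, with a stated focus on people with diabetes and African Americans over 50;
- same-day referral of diabetic patients when the technician has room;
- self-referral: "We will publicize the program in both free clinics using print media to open the program to self-referrals";
- information on the clinic websites, to make the programme better known in the community.

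The paragraph on no-show appointments says that the study is open to people outside the clinics, so that "potential participants may or may not be clinic patients". The paragraph on the baseline screening examination provides for registering them: a clinic record is not needed at Hope, but an account must be created at Hamilton. The introduction to Aim 2 adds: "We will offer both free glaucoma screening and a free eyeglasses exam".

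The only denominator spelled out, under the secondary prevalence outcomes, is everyone screened in the year. The Aim 2 Data Analysis text takes n = 5,800 and states that "the margin of error is at most 1.2 percentage points for the overall prevalence". It warns of larger margins only for annual and by-site estimates.

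**The concern.** The hypothesis names a setting, the primary care clinic, and contrasts it with general-population screening. The estimate comes from whoever was screened, including people who belong to neither clinic. If those people have a different prevalence from clinic patients, the pooled figure differs from clinic prevalence by an amount that enrolling more people does not reduce. A higher prevalence than in the general population could then reflect who came forward and not the clinic setting.

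The same holds for the secondary prevalences of visual impairment and refractive error, and for cost per detected case, which depends on the same yield. Because the protocol attaches one margin to an overall prevalence and mentions no other source of error, a reader could take 1.2 points as the full uncertainty about prevalence in the clinics.

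**Working it through.** **1. The plan's own margin.** Inputs: n = 5,800 (Aim 2 Data Analysis); 95% two-sided (assumed, since no level is stated). Half-width = 1.96 × √(p(1−p)/n).

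| Prevalence p | Half-width (points) |
|---|---|
| 0.20 | 1.03 |
| 0.30 | 1.18 |
| 0.32 | 1.20 |
| 0.38 | 1.25 |
| 0.42 | 1.27 |
| 0.50 (worst case) | 1.29 |

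The stated maximum of 1.2 is not reproduced: 1.96 × √(0.25/5,800) = 1.29 points. It holds for prevalences up to about 32%, or up to about 38% if rounded to one decimal. The two community programmes cited in the Background found glaucoma plus suspects in 17 + 21 = 38% and 19 + 23 = 42% of those screened, so prevalences in that region are plausible. A worst case of 1.2 would need about 6,669 participants. A finite population correction with N = 5,000 + 25,000 = 30,000 gives 1.29 × √(24,200/29,999) = 1.16, but the protocol states no such correction, and non-clinic participants lie outside that population.

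**2. What pooling can do.** Let s be the non-clinic share, p_c the prevalence in screened clinic patients and p_n that in non-clinic participants. Then

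pooled − p_c = (1−s)p_c + s·p_n − p_c = s × (p_n − p_c).

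The documents give neither s nor either prevalence, so all inputs here are assumptions:
- s = 25%, difference of 10 points in either direction: 0.25 × 10 = 2.5 points, up or down.
- s = 10% to 40%, absolute difference of 5 to 20 points: 0.10 × 5 = 0.5 to 0.40 × 20 = 8 points, up or down.
- No difference: no shift at any s.
- At s = 25%, the shift passes the worst-case margin once the difference exceeds 1.29/0.25 = 5.2 points.

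**3. Margin for existing clinic patients alone.** Share of 60% to 90% (assumed), p = 0.5:
- 90%: n = 5,220, 1.96 × √(0.25/5,220) = 1.36 points.
- 60%: n = 3,480, 1.96 × √(0.25/3,480) = 1.66 points.

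Against the corrected 1.29, separate reporting costs 0.07 to 0.37 points of precision.

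**4. Whether clinic status can be rebuilt later.** Hamilton provides 4,872 of the 7,320 new-screening slots (67%), and every non-clinic participant there must have an account. Holding a Hamilton record number therefore does not show that someone was a patient before the study.

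**The case against.** The strongest reply is that the protocol means yield throughout. The hypothesis speaks of what a programme will identify, the stated denominator is everyone screened, the Background benchmarks are percentages of those screened, and the other primary outcomes are number screened and cost per case. The clinic volumes open a capacity calculation and are never called a sampling frame. Much of this stands. It supports calling the pooled figure a yield, but it does not remove the mismatch with a hypothesis worded for clinics when some of those screened are not clinic patients.

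Three stronger readings are tempting and are not supported:
- *The margin does not apply at all.* A binomial half-width still describes sampling precision for the proportion among those screened. It fails only when read as covering error about clinic prevalence.
- *Prevalence is overstated.* The direction is unknown. Self-referral and the free eyeglasses exam may draw people with poor sight, though the protocol gives no figure for this and does not link the exam to glaucoma. Invited patients are deliberately risk-targeted, so self-referred or non-clinic people could equally lower glaucoma prevalence.
- *Patients called before appointments would give true clinic prevalence.* They are still risk-targeted volunteers, with a no-show and late-cancellation rate of about 35%, and known glaucoma counts as a positive screen.

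Self-referred and non-clinic are also different groups: the print media hang inside the clinics, so many self-referrals may be existing patients.

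Finally, part of the Data Analysis paragraph is missing from the text available, and subgroup reporting may sit in an analysis plan. That is why the point is confined to what is shown. An analysis plan cannot, however, reliably restore a recruitment route that was never recorded.

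**Conclusion.** The point holds in a limited form. The population named in the Aim 2 hypothesis and the group that supplies the estimate differ, and nothing shown separates them. The pooled figure is a screening yield, and its margin covers sampling error of that yield only. The size and sign of any departure from clinic prevalence cannot be found from the documents. The 2.5-point illustration rests on an assumed 25% non-clinic share and an assumed 10-point difference. It shows that the departure could be about twice the stated margin, not that it is.

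Separately, and with 95% confidence assumed, the stated maximum of 1.2 should be 1.3 (1.29). This is a small correction. The matter is worth fixing because it decides what Aim 2 may conclude about clinics; it does not undermine the screening programme or the yield itself.

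**What to change.** 1. Record recruitment route: pre-appointment call, same-day referral, or self-referral.
2. Record, as a separate field, whether the person was a patient of the clinic before the study. At Hamilton use the account-creation date or ask the participant, since an account alone does not show this. For people already enrolled, recover what the records allow and report the rest as unknown.
3. In the Aim 2 Outcomes and Data Analysis sections, call the pooled figure prevalence among those screened (screening yield).
4. Report prevalence, each with its own margin, for existing clinic patients (including those who self-refer) and for non-clinic participants. Use the clinic-patient figure for the Aim 2 hypothesis, and say that it still comes from a risk-targeted, voluntary group.
5. If the pooled margin is kept, state it as at most 1.3 points, name the confidence level, and say that it covers sampling error of the yield only.

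The cost is a small addition to data capture, some wording, and a somewhat wider margin for the clinic-patient estimate: 1.36 to 1.66 points in the worst case, if 90% to 60% of participants are clinic patients.
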